### **SUMMARY**

Immediately replacing fibrinogen in perioperative bleeding patients with acquired fibrinogen deficiency improves outcomes. The product that is primarily used for fibrinogen replacement in the US, cryoprecipitate, must be stored frozen and expires six hours after thawing, resulting in a delay in transfusion of approximately 50 minutes from the time it is ordered, as well as unnecessary transfusion of more readily available but not indicated blood components that are transfused while the patients waits for cryo. A modified version of the product, pathogen reduced (PR) cryo, is now FDA approved and can be thawed and stored for 5 days, allowing the product to be available immediately when needed. No clinical studies are available for this product. In this quality improvement study, we will compare the effect that readily available, pre-thawed PR cryo has on transfusion practice in cardiovascular and liver transplant patients who receive PR cryo versus those who receive traditional cryo by randomizing cryo transfusions in the blood bank by month to all cryo or all PR cryo. All clinical decisions, including the need for cryoprecipitate, and laboratory testing will occur per standard of care.

### INTRODUCTION

Cryoprecipitated AHF product (cryo), a pooled product from 5-10 blood donors, is the primary source of fibrinogen replacement for bleeding patients in the United States. When stored frozen, it has a shelf life of one year; however, it must be thawed prior to use. Thawing, labeling and dispensing cryo can take 28-97 minutes and then it must be transfused within 6 hours due to a theoretical risk of bacterial contamination.

The competing need to have cryo rapidly available for urgent transfusions and the need to avoid wasting product has led to the development of pathogen reduced (PR) cryo, which recently received FDA approval. This product is also called Intercept Fibrinogen Complex (IFC) and can be kept thawed at room temperature for up to 5 days after thawing.

PR cryoprecipitate is derived from a traditional cryoprecipitate product that is treated with amotosalen.

The inactivation of pathogens

[figure not shown]
allows thawed PR cryo to have a shelf-life of 5 days without the risk of microbial contamination. Furthermore, multiple studies have shown that fibrinogen is stable when thawed at room temperature for up to 35 days. The longer shelf-life should reduce product wastage which

would offset the increased cost of PR cryo over traditional cryo. In vitro studies have shown no differences in efficacy between traditional and PR cryo. No safety differences are expected between the two products, as evidenced by the FDA approving PR cryo without any clinical studies.

The same pathogen reduction process used for PR cryo/IFC that was developed by Cerus Corporation has been in use in the United States since 2014 for platelet and plasma products. Cryoprecipitate is a derivative of plasma, and the pathogen reduction process was already FDA approved. Therefore, the FDA approved this blood product and its pathogen inactivation process, without any clinical trials or observational studies.

PR cryo/IFC, the product we are studying, is a biological blood component and the process used to treat PR cryo, known as INTERCEPT® Blood System for Cryoprecipitation (package insert included in IRB application) is the same process used for PR platelets and PR plasma. The pathogen reduction process occurs at the blood supplier and then the product is received by

[figure not shown]

[figure not shown]
Since PR cryo can be kept at room temperature for 5 days, similar to thawed plasma, the blood bank can opt to have a PR cryo supply thawed and immediately available for use. This can prevent delays in treatment in bleeding patients.

# BACKGROUND OF CRYO USE AT NYP/WC

Given PR cryo's recent FDA approval, no real-world studies or clinical trials exist directly comparing conventional cryoprecipitate and pathogen reduced cryoprecipitate use in the perioperative setting. The relative frequency of cryoprecipitate usage in our large cardiac and

liver transplant programs at Weill Cornell provides an ideal setting to compare the two products.

### **STUDY DESIGN**

Given that PR cryo can be more readily available for urgent perioperative need, the transfusion medicine service and anesthesiologists at NYP/WC would like to transition to this product. PR cryo is a more expensive product, so it is necessary to evaluate whether its availability will reduce the need for other blood products or reduce traditional cryo wastage, prior to fully converting to this product. A single center prospective, pilot cluster randomized study with an adaptive design will be used to compare the availability and cost effectiveness of cryo and PR cryo when it is ordered for standard clinical indications. In this design, the intervention and randomization are not made at the level of the individual patient, but rather on clusters of patients by month. The clusters will include all patients at NYP/WC for whom pooled cryo is ordered during a single month, not just liver transplant and cardiovascular surgery patients.

Since both products are considered clinically equivalent, the blood bank will alternate use of PR cryo and regular cryo each month for all patients with a cryo order over a one year period during the transition to the use of this new product. All patients will receive either traditional cryo or PR cryo in a given month; however, only a subset (CV and LT patients) will be studied.

Data from the EMR and lab systems will be collected from the NYP data warehouse during the one-year QA study and included in the data analysis. The following demographic variables will be collected: age, ethnicity, race, gender, underlying diseases, surgery type, medications given within 5 days of surgery.

The primary outcome will be the total number of blood components (RBCs, platelets, plasma) used over the admission within the first 30 days after surgery.

REDCap will be used for data collection/storage. Our data scientist, who is an Epic Clinical Data Navigator (CDN), will use SQL queries through the NYP Jupiter data warehouse for automated data extractions of clinical and laboratory data. A TRAC request will be submitted once the IRB is approved. Any variables not available through Jupiter will be extracted manually from the electronic medical record by the research coordinator and entered manually in REDCap. We will use the Safe Harbor method for de-identification of data. We will remove all 18 PHI elements referenced by HHS that could identify a patient.

The secondary outcomes, which are all routinely available in the EMR per standard of care, will include:

1. Number of cryo or fibrinogen concentrate products used perioperatively (defined as anesthesia start time to 3 days post-procedure)

- 2. Number of RBC, plasma, and platelet products used perioperatively (defined as anesthesia start time to 3 days post-procedure)
- 3. Time from OR start time to start of cryo transfusion
- 4. Time from cryo order to start of transfusion
- 5. Number of cryo units wasted by blood bank per month during study periods.
- 6. Laboratory measures, as available in the medical record, related to the indications for cryo: pre and post transfusion FIBTEM amplitude at 10 mins and maximum clot firmness & fibrinogen level within 10 minutes to one hour after the end of the first cryo transfusion.
- 7. Highest and lowest fibrinogen level or ROTEM FIBTEM within 24 hours after surgery.
- 8. Volume in drains (e.g. chest tube for CV surgery) at 24 hours or until removed, whichever is sooner.
- Time from end of bypass pump until end of surgery (reflects time to hemostasis) for CV surgery
- 10. Length of stay (OR, ICU and hospital)
- 11. Need for ventilator
- 12. Time on ventilator
- 13. Overall cost of cryo vs PR cryo, when factoring wastage, during each 1-month period
- 14. Adverse events: fevers, infections, transfusion reactions within 5 days of surgery start time, need for surgical re-exploration, multiorgan system failure
- 15. Fibrinogen level most proximal to end of procedure

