### STUDY PATIENT POPULATION

Liver transplant and cardiovascular surgery populations were chosen because they are the 2 patient populations which receive cryo during massive blood loss most frequently in the operating room. Although they don't have the same mechanisms of injury and coagulation dysregulation, they both are prone to severe and early hypofibrinogenemia, hyperfibrinolysis, thrombocytopenia, platelet dysfunction and dilutional coagulopathy during surgery. The CV surgery and liver transplant anesthesiology groups at Weill Cornell faithfully use ROTEM for real time goal directed blood product therapy. Other patient populations may receive cryo, but cryo tends to be less predictably used in these populations, less evidence based (i.e., less based on immediately available point of care coagulation lab results) and more of a last resort option, rather than an early planned intervention. The other groups of patients who require cryo are smaller, more heterogeneous and have more covariates that will make data analysis more difficult to interpret. Thus, the focus is on two fairly homogeneous patient groups at high probability to require cryo transfusion.

Inclusion criteria: Adult patients undergoing cardiovascular surgery or liver transplant who receive cryo during surgery during the two year study period. Cardiovascular surgery includes the following procedures: coronary artery bypass grafting, valve repair or replacement, open thoracic aortic and thoracoabdominal aortic surgery, atrial or ventricular septal defects, ventricular assist device implantation or revision, or any combination of the above.

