### STATISTICAL ANALYSIS

#### RATIONALE FOR A CLUSTER RANDOMIZED TRIAL

Individual patient efficacy clinical trials are useful to establish the clinical efficacy of an intervention amongst a carefully selected population under optimal conditions following detailed protocols. However, such trials do not address questions about how an intervention or logistical change affects clinical practice in the real world.

The surgical care of patients in our hospital is undertaken using standardized procedures that optimize outcomes, such as standard preoperative assessment and pre-and postoperative care pathways. Because our cardiac surgery and liver transplant services deliver care through standard institutional policies, it is appropriate to address whether either of the two FDAapproved blood products for fibrinogen replacement in acquired hypofibrinogenemia used during surgery to treat bleeding would reduce the total amount of blood products transfused. Testing the effects of the two products mandates a pragmatic trial done with randomization of product used by month rather than by patient. It is extremely difficult to predict which patients will receive fibrinogen replacement during surgery and thus impossible to predict which patients to consent ahead of time. At the time the decision is made to transfuse cryoprecipitate, a patient is already bleeding and under anesthesia, and thus there is no opportunity to consent in real time. Thus, this study will use a cluster randomization treatment assignment design with a calendar month time period as the cluster; specifically addressing whether the use of cryoprecipitate or PR cryoprecipitate reduces overall blood transfusions without any contamination of study groups by the inability to fulfill the appropriate cryo use if individual randomization had been used.

The main challenge of a cluster-randomized trial is the need for inflated sample size (relative to a non-clustered design) that results from clustering. Individuals within a cluster tend to have a smaller degree of variation compared to the variation between clusters, which is measured statistically by the intra-cluster correlation coefficient (ICC) (Arnup SJ et al). If the ICC is greater than 1, then this cluster effect will incorrectly reduce the standard error of the model estimates

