if it is not properly accounted for in the analysis. This study will use randomization between intervention arms each month with a design known as the cluster randomized trial. This allows for the ability to assure that all research subjects in a given month will receive a particular cryo product and ensure the reduction in contamination of the two study arms (one of the primary reasons for designing studies in this fashion). In the planned trial, each month the Weill Cornell blood bank will be randomized to one of the two cryoprecipitates as part of a quality improvement study, the randomized product will be used as standard institutional policy for an entire calendar month. At the end of each month, the blood bank is re-randomized to a new standard policy that is used for the subsequent calendar month. This design is methodologically rigorous and tests the effect of a change in standard policy as it would actually be used in the clinical setting.

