#### **SAMPLE SIZE ANALYSIS**

The primary endpoint of the study is total number of blood components other than cryo (RBCs, platelets, plasma) used over the hospital admission within the first 30 days after surgery. The goal of the trial is to demonstrate a 20% reduction in this total blood product use for PR cryo compared to the total observed with conventional cryo. In order to determine this effect size and the patient variability associated with this outcome, data were collected from 150 cardiovascular surgery and liver transplant cases at the study center during 6 months in 2021. Because the number of units used was clearly right-skewed and, therefore, possibly lognormally distributed, the sample size determination was based on the hypothesized ratio of means (effect size) of 0.8. In addition, the coefficient of variation is the key determinant of variability with log-normal data, and this was seen with the recent data to be a value of 1.1. The other issue to consider in this calculation is the cluster randomization. However, the cluster in this study is the month when the surgery is performed. The assumption is made that the intracluster correlation of the primary outcome within a given month should be very small, say 0.0001. As a result, this would have very little effect on the sample size (the Kish design effect is about 1.01 assuming approximately 100 subjects per month). Then with 80% power and 5% significance (two-sided), the number of subjects per group would be 251.

However, there is a possibility that the effect size has been overestimated. Thus, a sample size re-estimation will be conducted after 60% of the subjects have been included in the trial. The method of Gould (Gould AL. Interim analyses for monitoring clinical trials that do not materially affect the type I error rate. Stat Med 1992; 11:55-66.) will be used to re-evaluate the sample size.

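### The plan says both that the product alternates by month and that it is re-randomized by month; it gives no sequence method, so the allocation rule is undefined

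*Combined protocol and SAP*

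**What the plan says.** The combined protocol and SAP describes allocation in several places.

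- Summary: the study compares products by "randomizing cryo transfusions in the blood bank by month to all cryo or all PR cryo".
- Study Design: the study is called cluster randomized by month, but the next paragraph says "the blood bank will alternate use of PR cryo and regular cryo each month".
- Rationale for a Cluster Randomized Trial: the study uses a "cluster randomization treatment assignment design with a calendar month time period as the cluster"; "each month the Weill Cornell blood bank will be randomized to one of the two cryoprecipitates"; and "At the end of each month, the blood bank is re-randomized to a new standard policy".
- Sample Size Analysis: "the number of subjects per group would be 251". Interim Analysis repeats this as 502 in total, so equal arms are assumed.
- Evaluation of Product Superiority: the primary test is a two-sample t-test on log values, or a Wilcoxon rank-sum test. It has no term for month or calendar time. Covariate adjustment is mentioned only as a possibility.

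The length of the study, and so the number of months to allocate, also varies. Study Design has allocation running "for all patients with a cryo order over a one year period", while the inclusion criteria cover patients "who receive cryo during surgery during the two year study period". Interim Analysis expects 302 patients in about a year, which puts 502 at about 20 months.

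**The concern.** The month is the unit of randomization, so the rule that assigns months decides whether this is a randomized trial and what protects it against trends over time. The two descriptions have different weaknesses.

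Under strict alternation, the first month fixes all the others. Teams would know the product for every future month, and the claim of randomization month by month would not be met. A test based on the randomization would have only two possible sequences to refer to.

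Under a fresh, unrestricted draw each month, nothing holds the two products to equal numbers of months or spreads them evenly over the calendar. Unequal months mean unequal arms, against a sample size built on equal ones. A run of one product early or late would let a trend or season in transfusion practice pass straight into an unadjusted comparison.

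Allocation cannot be repaired once months have been assigned, so the rule has to be settled before the first one.

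**Working it through.** **Inputs.** Ratio of means 0.8, coefficient of variation 1.1, two-sided 5%, 80% power, 251 per group (Sample Size Analysis). Accrual of 302 per year (Interim Analysis), so 302/12 ≈ 25 per month and 502/25.17 ≈ 20 months. Because the documents disagree on duration, 12, 20 and 24 months are all shown.

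**The plan's own figure.** Log-scale variance = ln(1 + 1.1²) = 0.793, SD 0.8905; difference = |ln 0.8| = 0.2231. Then n = 2 × 0.793 × (1.960 + 0.842)² / 0.2231² = 250 per group. The noncentral-t version gives 251, and multiplying the normal figure by the design effect of 1.0099 gives 253. The stated 251 is reproduced.

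**Alternation.** There are two possible sequences, one for each starting product. Over an even number of months the split is exactly equal, and the arms' mean calendar months differ by 1. Every month after the first is known.

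**Unrestricted monthly randomization.** This is an assumption: the plan states no restriction, but does not say that there is none. For K months:

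- P(equal split) = C(K, K/2) / 2^K.
- Power at k versus K − k months = Φ(0.2231 / √(0.793 (1/n₁ + 1/n₂)) − 1.96), with n₁ = 502k/K and n₂ = 502 − n₁. This assumes equal accrual per month and ignores clustering. Average power weights each split by its binomial probability.
- Calendar gap = absolute difference between the arms' mean month number, over all sequences that use both products.

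| | 12 months | 20 months | 24 months |
|---|---|---|---|
| P(equal split) | 22.6% | 17.6% | 16.1% |
| Power at an equal split | 80.2% | 80.2% | 80.2% |
| Average power | 76.2% | 77.9% | 78.3% |
| SD of difference in mean month | 2.2 | 2.7 | 3.0 |
| P(gap more than 3 months) | 15.9% | 27.1% | 31.1% |

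Individual splits show where power is lost. At 20 months, 7:13 or worse has probability 26.3%, and power at 7:13 is 76.4%; 6:14 or worse has probability 11.5%, and power at 6:14 is 73.0%. At 12 months, 4:8 or worse has probability 38.8%, and power at 4:8 is 75.4%; 3:9 or worse has probability 14.6%, and power at 3:9 is 68.1%. The 12-month power figures hold the total at 502, whereas the plan's accrual gives about 302 in a year. They isolate the effect of the split and do not forecast a one-year study.

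**Permuted blocks, for comparison.** Blocks of 2 months give equal counts, a calendar gap of at most 1 month, and 2⁶ = 64 sequences over 12 months. Blocks of 4 give equal counts, a gap of at most 2 months, and 6³ = 216 sequences over 12 months (6⁵ = 7,776 over 20). Predictable months: with blocks of 2, the second of each pair, so one half. With blocks of 4, the last month always, and the third as well when the first two match (probability 1/3), so (1 + 1/3)/4 = 1/3 on average.

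**The case against.** The best defence is that the conflict is one clause against the rest. Every other description, including the paragraph just before the clause, speaks of randomization by month. The verb may be loose wording for switching between products. That is plausible, but no section confirms it. If it is so, the plan still lacks a sequence method and any restriction.

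Four stronger readings are tempting, and the documents do not support them.

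- *That re-randomization will leave the arms unbalanced.* Imbalance is likely, not certain, and only if the draw is unrestricted.
- *That the trial loses serious power.* Average loss against 80.2% is about 4 points at 12 months and 2 at 20 or 24. It becomes material only at the more extreme splits.
- *That advance knowledge of the product lets clinicians choose who enters.* Inclusion does depend on receiving cryo. However, the plan describes no masking, and PR cryo is meant to be thawed and at hand, so the current month's product can be known under any rule. Foreknowledge of later months bears mainly on scheduling, and the plan says that the need for fibrinogen replacement cannot be accurately predicted before surgery.
- *That an uneven split puts month-level endpoints beyond the Holm threshold.* At 3:9 the smallest Wilcoxon p is 2/C(12,3) = 2/220 = 0.009, above 0.05/10 = 0.005. But 0.005 is only the first Holm step, and monthly cost is the only endpoint that the analysis section explicitly sets per month.

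It also stands that alternation controls trend well: its 1-month calendar gap equals the maximum under blocks of 2. Confounding with calendar time is a concern for unrestricted randomization only.

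**Conclusion.** The contradiction stands and should be resolved before allocation begins. As written, the blood bank cannot tell which rule to follow, and a reader cannot tell whether months are randomized. Under alternation, the study would be balanced but not randomized month by month as it claims. Under unrestricted re-randomization, it would be randomized but open to imbalance: the chance of unequal month counts is 77% to 84%, average power is about 76% to 78%, and the calendar gap exceeds 3 months in 16% to 31% of sequences, across 12 to 24 months. The calendar gap matters more than the power loss because the primary test has no time term. How much bias it would cause depends on trends in transfusion practice, about which the documents give no figures.

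These figures assume equal monthly accrual, 502 patients, no clustering and an unrestricted draw. The need for a correction rests on the undefined allocation rule and not on the power figures.

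**What to change.** Replace both statements with one rule, used wherever allocation is described:

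- Allocate calendar months by restricted randomization in permuted blocks of consecutive months, of size 4 or a mix of 2 and 4.
- Have the statistician generate the whole list in advance, with spare blocks in case the sample-size re-estimation extends the trial, and release each month's product to the blood bank only at the changeover.
- State the planned number of months, reconciling the one-year and two-year wording.
- Reflect the blocks in the analysis, for example as a block term in the primary model or a randomization test that permutes within blocks.

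The cost is one paragraph, a short list and a modest change to the analysis text. The downsides should be stated. Some months remain predictable: half with blocks of 2, about one third with blocks of 4. Blocks of 4 also allow a calendar gap of up to 2 months instead of 1. Concealing later months does not hide the current month's product from the clinicians who decide to give cryo.

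### The plan gives both one year and two years as the study duration, and one year cannot deliver the planned 502 patients at its own accrual rate

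*Combined protocol and SAP*

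**What the plan says.** The combined protocol and SAP gives the length of the study in three places.

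- **STUDY DESIGN** says one year twice. Monthly alternation of the two products applies "for all patients with a cryo order over a one year period during the transition", and the study data "will be collected from the NYP data warehouse during the one-year QA study and included in the data analysis". The same section describes the study as a "pilot cluster randomized study with an adaptive design".
- **STUDY PATIENT POPULATION** makes patients eligible "who receive cryo during surgery during the two year study period".
- **INTERIM ANALYSIS** takes 302 as 60% of 502, expects that number in roughly one year, and places there a decision to continue or stop, with a possible stopping rule of conditional power below 10%.

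The size of the trial is set by patient number in SAMPLE SIZE ANALYSIS: "Then with 80% power and 5% significance (two-sided), the number of subjects per group would be 251". Because "there is a possibility that the effect size has been overestimated", that section adds that "a sample size re-estimation will be conducted after 60% of the subjects have been included in the trial".

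SAMPLE SIZE ANALYSIS also holds two figures that bear on accrual: 150 cases at the centre in six months of 2021, and a design effect that assumes about 100 subjects per month.

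**The concern.** These statements cannot all describe the same study. If 302 patients are expected in the first year and 502 are needed, allocation and data collection must run past the year given in STUDY DESIGN. A study that ends at one year has nothing left to continue after the interim.

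STUDY DESIGN is the section that tells the blood bank how long to alternate products and the data team how long to extract records. If its calendar were followed:

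- the study would end at about the interim count;
- the re-estimation, included as protection against an optimistic effect size, could not enlarge the trial within that year;
- a patient operated on in month 15 would meet the inclusion criteria but fall outside the allocation and data-collection period.

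**Working it through.** **Inputs.** From SAMPLE SIZE ANALYSIS: ratio of means 0.8, coefficient of variation 1.1, two-sided 5%, 80% power, 251 per group, intracluster correlation 0.0001, about 100 subjects per month, 150 cases in 6 months. From INTERIM ANALYSIS: 502 in total, 302 in about one year. Assumptions made here: equal arms and a patient-level t-test on logs, which is the plan's first-choice analysis.

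**1. Reproduce the plan's size.**
- Log-scale variance = ln(1 + 1.1²) = 0.7930, so SD = 0.8905.
- Log difference = |ln 0.8| = 0.2231.
- n per group = 2 × [SD × (1.960 + 0.842) / 0.2231]² = 250 by the normal approximation. The noncentral t gives 251.
- Power at 251 per group is 80.0%. The stated figure reproduces.

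**2. Time to reach 502.**
- Rate: 302 / 12 = 25.2 per month.
- 502 / 25.17 = 19.9 months.
- After the 302nd patient: (502 − 302) / 25.17 = 7.9 months.
- Rate needed for 502 in 12 months: 502 / 12 = 41.8 per month, or 1.66 times the forecast.
- The 2021 data agree with the forecast: 150 / 6 = 25 per month.

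**3. If the study ended at one year.**
- 302 patients, 151 per group: power 58.3% (noncentral t).
- With the plan's design effect, 1 + 99 × 0.0001 = 1.0099, power is 57.9%, against 79.6% at 251 per group. The conclusion does not change.
- The ratio detectable with 80% power at 151 per group is 0.75, a 25% reduction.
- An unequal split of months lowers power a little further. By the normal approximation it is 57.4% for 5 against 7 months and 53.7% for 4 against 8, compared with 58.6% for 6 against 6.

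**4. Sensitivity to the rate.** The forecast is approximate, so take 20% either side as an assumption.

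| Rate per month | Patients in one year | Power at one year | Months to 502 |
|---|---|---|---|
| 20.1 (−20%) | 242 | 49% | 24.9 |
| 25.2 | 302 | 58% | 19.9 |
| 30.2 (+20%) | 362 | 66% | 16.6 |

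One year falls short of 502 throughout. At the slow end, two years also falls slightly short.

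**5. The 60% looks.** At 25.2 per month the 302nd patient arrives at month 12, so both looks fall at or after the last patient of a one-year study. At the slow rate 302 is not reached within the year. At the fast rate it comes at 302 / 30.2 = 10 months, but the year still ends at 362, well below 502.

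**6. The other monthly figure.** At 100 study patients per month, 502 would be reached in about 5 months. That is four times both the INTERIM ANALYSIS forecast and the 2021 volume.

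**The case against.** The best defence is that the operative text already settles the matter. The trial is sized by patient number, INTERIM ANALYSIS says what happens at 302 patients, and no section gives a calendar stopping rule. The inclusion criteria, SAMPLE SIZE ANALYSIS and INTERIM ANALYSIS agree with one another, since 20 months fits inside two years. STUDY DESIGN itself calls the design adaptive, and its year matches the expected time to the interim, so it may mean only the first stage. Much of this stands. It shows which statement is the outlier, and it means that the planned number is not itself wrong. But STUDY DESIGN never says that its year is a first stage, and it applies the term one-year to the study as a whole.

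Three stronger readings are tempting and are not supported.

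- *The trial has only 58% power.* That follows only if the year in STUDY DESIGN overrides the other three sections. If they govern, duration costs no power at the forecast rate.
- *The interim cannot take place until every one of the 302 patients has passed day 30.* The primary outcome counts components "used over the admission within the first 30 days after surgery", so counting is confined to the admission. A patient discharged earlier is complete at discharge, and the INTERIM ANALYSIS timing is approximate in any case.
- *The 100-per-month figure rescues the one-year plan.* It appears only as a cluster size in the design effect and conflicts with the explicit forecast and with the 2021 volume. It may count all cryo recipients, but the text does not say so.

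**Conclusion.** The contradiction is real and unreconciled in the current text. At the plan's own rate of about 25 patients per month, 502 patients need about 20 months. The one-year statements in STUDY DESIGN are therefore incompatible with the planned 251 per group and with an interim that can change the course of the study. The two-year period is compatible with both at that rate.

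The size of the consequence is conditional. Power of about 58% (49% to 66% over the assumed rate range), against 80% planned, applies only if the year is enforced as the end of the study. It also rests on equal arms and on the plan's own effect size, variability and negligible within-month correlation. What the documents establish without condition is that the period of allocation, data collection and eligibility is not defined consistently.

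**What to change.** - **STUDY DESIGN.** Replace both one-year statements with a period defined by number: until 502 patients, or the re-estimated number, are accrued; expected to take about 20 months. If the year is meant only as the stage up to the interim, say so there instead.
- **STUDY PATIENT POPULATION.** Tie the eligibility window to that same accrual period. State which limit governs if the target is not reached within two years. At the INTERIM ANALYSIS rate two years yields about 2 × 302 = 604 patients, so a larger re-estimated number would not fit. At a rate 20% lower, even 502 takes 24.9 months.
- **SAMPLE SIZE ANALYSIS.** Reconcile the 100 subjects per month with the forecast of about 25, or state which patients it counts. With 25.2 per month the design effect becomes 1 + 24.2 × 0.0001 = 1.0024, so at the assumed intracluster correlation the sample size hardly moves.
- **If a one-year study is intended,** restate the power as about 58% and bring the two-year eligibility period into line.

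The cost of the main option is a few changes of wording, plus allocation and data collection for about 8 months beyond the year now stated (200 further patients at 25.2 per month). The one-year option saves that time, at the price of openly planning for about 58% power.
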